5.4 UNBLINDING THE TRIAL

Once the analysis detailed in this SAP has been executed procedures for unblinding the trial statistician will follow NWORTH SOP 5.03. Once the results of the analysis have been reported to the TMG and with approval from NWORTH Principal Statistician, the trial statistician will request unblinding from NWORTH IT. The CI of the trial will be informed that the trial statistician is to be unblinded. In line with SOP 5.03, a form will be completed and sent to NWORTH IT who will then inform the statistician of the group allocation details.

6. STATISTICAL ANALYSES

6.1 ANALYSIS TIME FRAME

Table 3. Dianned target timeline for anal	voic dependent on recruitment period
Table 3: Planned target timeline for anal	vsis dependent on recruitment period

Task	Planned time frame in line with study closeout
Last patient recruited	January 2021
Final patient visit	July 2021
*Database Lock	~August 2021
*Analysis	~September 2021

*Database lock will occur 30 days following final patient visit, given data cleaning has been finalised and all queries dealt with. Analysis report will be finalised and sent to the study team within one month from data lock.

6.2 BLIND REVIEW OF THE DATA

The outcomes for this study are continuous measures and we would not envisage any major issues that would require a deviation from analysis. The assumptions for the models will be checked as indicated in section 4.7. Given this and the nature of the analysis, we will not be doing a blind review of the data. Any deviations from the intended analysis along with any transformations or assumptions violated will be described and fully justified in the write up of the analysis report.

6.3 BASELINE ANALYSIS

Demographics and patient characteristics collected at baseline will be presented descriptively both overall and by treatment arm. No statistical testing of baseline differences will be completed, only to visually assess balance (de Boer et al., 2015; Moher, 2010). Continuous variables will be reported with mean values, standard deviations and ranges. Categorical variables will be presented with counts and percentages. If data are not normally distributed, then medians and interquartile ranges will be reported.

6.4 INTERIM ANALYSIS

There are no planned interim analyses and as such the study is not powered to achieve these.

6.5 CONSORT ANALYSIS

The patient flow information, shown in section 3.3 as advised by CONSORT reporting standards (Schulz et al., 2010), will be completed with values relating to participants numbers. Data will be presented on screening, eligibility, recruitment, treatment discontinuation, study withdrawals and lost to follow up, presented for the entire study and split by recruitment site. Where possible, reasons for ineligibility, non-recruitment, treatment discontinuation and withdrawal will be reported. From these data related eligibility, recruitment and retention rates will be calculated and presented.

6.6 DESCRIPTIVE STATISTICS

Descriptive statistics of the data will be presented in the final analysis report. This will include randomisation figures, demographics, other data characteristics of the outcome measures and data completeness levels. All will be presented overall and split by allocation group.

Figures will be presented for the Randomisation data by each stratification variable;

- Allocation group
- Centre

- Gender (Sex at birth)
- Type of ward

The following demographics and data characteristics will be presented;

- Ethnicity
- Gender (self-identified)
- Age
- ICD-10 codes current admission and previous admission
- IPDE scores

Descriptive statistics of the primary outcome measures will be produced, these will be presented overall and split by allocation group. Additionally, the primary outcome descriptive statistics at baseline will be split by ward type. Furthermore, 3 and 6 months by trial arm allocation perception, see section 6.10 for more details. Descriptive statistics of the secondary outcome variables as listed in table 2will also be presented (overall and split by group).

For all statistics, continuous variables will be reported with mean values, standard deviations and ranges. Categorical variables will be presented with counts and percentages. If data are not normally distributed, then medians and interquartile ranges will be reported.

6.7 ANALYSIS OF PRIMARY OUTCOME

The intention for the study was to analyse the primary outcome using model general linear model fitted at six months and adjusted for baseline score, allocation group and randomisation stratification variables (centre, gender and ward type). Additional covariates would have also been considered.

Due to the small sample, the primary outcome will be analysed, with a general linear model at six months adjusted for baseline score only along with site as a random effect. With such little data including all the intended variables (randomisation stratification variables) in the model would likely result in overfitting the data. Thus, this model in its most simple form seems the most reasonable analysis to assess the research question given the small sample. The study will not be statistically powered, and results will be interpreted with caution.

Primary analysis will be with the mITT dataset. However, further exploratory analysis consisting of a per protocol analysis will be conducted on the primary outcome as indicated in section 6.10.

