2. STATISTICAL ANALYSIS PLAN AUTHORSHIP

This SAP has been authored by [name] (Senior Statistician NWORTH CTU), Trial Statistician for the CALMED Trial, with input from [name], Senior Trial Statistician for the trial (Principal Statistician NWORTH CTU), [name] (Chief Investigator) and [name] (Trial Manager).

The study began recruitment in September 2019 however, due to several difficulties such as recruiting in this population and the impacts of COVID-19, which are still ongoing, the study struggled to reach recruitment targets. Efforts were made to increase recruitment to the study but unfortunately recruitment to the study remained an issue.

The sample size of the study was re-calculated and reduced, see section 4.1, however in March 2021, with agreement from independent committees and the funder, the study was terminated. At the time of termination, a final sample of 29 randomised patients was reached.

This document details the planned analysis according to the protocol, given the full sample, and the analysis that will be carried out for the study given the sample reached. It should be noted that the sample is very small, and far below the statistical power required to evaluate the intended research question. Therefore, all results presented following the analysis should be interpreted with caution.

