222 inpatients with BPD will be recruited from seven centres in England over a 24-month period. All participants will be followed-up at three and six months using a battery of assessment scales to measure mental health (Zanarini rating scale for Borderline Personality Disorder - ZAN-BPD, and the Brief Psychiatric rating Scale - BPRS), incidence of violence to self or others (MOAS), acts of deliberate self-harm, health-related quality of life (EQ-5D-3L), side effects of treatment, adherence and adverse reactions. Resource use and costs will be assessed using a modified version of the Adult Service Use Schedule and with nationally available unit costs. We will continue to collect economic data from clinical records on use and type of inpatient treatment, use of community services and quantity and type of medication that participants take throughout the study. We will use a flexible dosing regimen of clozapine. Dosing will start with 12.5 mg once daily and be titrated to 300mg over a 15-day period. Study participants may be prescribed a dose of up to 400mg of clozapine daily, depending on clinical response, patient preference and side effects. The dose may be

maintained at or reduced to a lower dose at any time. Equivalent numbers of placebo capsules will be administered to participants in the control arm of the trial. All those taking part in the study will continue to receive all other treatments as usual.

The trial will involve two linked phases:

Phase 1 - An internal pilot in which participants will be recruited from all centres over a sixmonth period. Data from the internal pilot will be presented to the Trial Steering Committee (TSC) indexed against a priori stop/go criteria, that will be used to determine if the study progresses to phase 2.

Phase 2 - Full trial across all sites over a further 18-month period.

Progression criteria will be assessed at six months according to the following three parameters:

- Number of participants randomised in the first six months. Our target is 55. If above 42 (75% of the target) recruitment would continue. If between 35 and 41 we would discuss continuation with the independent committees and funder. If below 32 (less than 60% of the target) we would stop. Mitigating circumstances for under-recruitment such as a delay in opening one or more of the pilot sites will be discussed with the TSC and may result in an adjustment to the participant target or pilot period.

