4.3 LEVELS OF CONFIDENCE AND P-VALUES

All statistical tests for the primary endpoints will be two-sided and will be performed using a 5% significance level. Confidence intervals for estimated effects will be presented as 95% and two-sided. As this study will not provide conclusive evidence and will lack statistical power, secondary outcomes will not be adjusted for multiple comparisons. Results will be interpreted with caution, 95% confidence intervals will be reported alongside any p-value or effect.

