4.6 MISSING DATA

Missing observations are expected within the dataset. Completion rates of outcome measures will be summarised in the final analysis report, at the item and overall level.

Missing data – outcome item level

For missing items within an outcome measure, the published rules for completing missing data for the relevant measure will be applied. Where there are no missing data rules for the measure, if the number of missing items on an outcome measure is 20% or less, then the missing value for the item will be substituted by the individual's mean score for the remaining items on the scale (Bono, Ried, Kimberlin and Vogel 2007). If there are more than 20% missing items in the scale the outcome measure will not be calculated for the participant at that time point.

Missing data -outcome total score level

A missing completely at random test devised by Little (1998) will be performed to assess whether the data is missing completely at random (MCAR). If this test indicates that data is missing completely at random than analyses will be based on complete cases, else independent t-tests will be conducted to investigate whether the data is missing at random (MAR). If these tests suggest that the missing data is MAR, then predictive mean matching multiple imputation method will be employed. Otherwise, additional modelling guided by clinical knowledge would be required to simulate the missing data mechanism and impute the missing data.

Analysis will be conducted using multiple imputation for the primary and secondary analysis outcome measures. Complete case analysis will be conducted as sensitivity analysis (see section 6.10) to check the impacts that missing data may have had on the results, this is especially important given the small sample and high withdrawal (in relation to the sample) rate.

For imputation, predictive mean matching multiple imputation methods will be adopted. For multiple imputations, the number of imputations completed is dependent upon the percentage of missing data (White, Royston, & Wood, 2011). The current dataset has 18% of the primary outcome missing, which would require 18 imputation sets, which is very large given the total study sample, therefore, the number of imputations with this sample will be limited to m=5, White (2011) state that "Standard texts on multiple imputation suggest that small numbers of imputed data sets (m =3 or 5) are adequate".

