4.8 ANALYSIS SETS

All primary analysis will be using modified ITT analysis (mITT), in which all randomised participants will be included who have taken at least one dose of trial medication.

For participants that were randomised but did not take any trial medication, they will be included in summary descriptive statistics only as they are not part of the mITT dataset (see figure 1).

A per protocol analysis set will also be used. This will consist of participants who took trial medication, at least until the first follow-up at 3 months. i.e. all those in the mITT set who withdrew from trial medication prior to their 3 month follow up are removed in addition to the participants randomised that didn't take trial medication at all.

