7. SOFTWARE

All quantitative analysis will be completed using STATA version 15 or later.

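### Section 6.7 fits a random-site mixed model to about 23–29 patients without fixing any small-sample inference, so the 5% level and 95% coverage promised in 4.3 are not secured

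*SAP*

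**What the plan says.** Section 6.7 drops the stratification covariates because of the small sample and fits the six-month score with a linear model "adjusted for baseline score only along with site as a random effect". Section 6.8 carries this model to the secondary outcomes, except the adherence scale, which gets t-tests.

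Section 4.3 sets the standard: "All statistical tests for the primary endpoints will be two-sided and will be performed using a 5% significance level", with two-sided 95% intervals.

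The sample is fixed elsewhere. Section 2 reports that "a final sample of 29 randomised patients was reached". Section 4.8 limits the primary set to a modified intention-to-treat set in which "all randomised participants will be included who have taken at least one dose of trial medication". Section 4.6 states that "The current dataset has 18% of the primary outcome missing", makes multiple imputation the main analysis with complete cases as a sensitivity analysis, and says that "the number of imputations with this sample will be limited to m=5".

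On implementation, section 7 says only that "All quantitative analysis will be completed using STATA version 15 or later". Nothing in the SAP names ML or REML, a z or t reference, a degrees-of-freedom method for the mixed model, or one for pooling imputations. The checks in section 4.7 concern residuals, collinearity and outliers.

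**The concern.** For an ordinary ANCOVA, silence on inference is harmless, because there is one standard t-test and it is exact under normal errors. A random site effect removes that default. The analyst must then choose an estimator and a reference distribution, and with two dozen patients in a handful of sites the choice changes the p-value and the interval. ML divides the residual variance by n rather than by its degrees of freedom, and a z reference treats the variance as known. Both make intervals too short.

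Pooling five imputations raises the same problem again, because Rubin's usual degrees of freedom assume a large complete-data sample.

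At stake is whether the reported 95% intervals have their stated coverage, for the primary outcome and for several secondary outcomes. A choice left open until analysis is also one that could be made after results are seen.

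**Working it through.** **Inputs from the SAP**
- Level 5%, two-sided (4.3).
- 29 randomised (section 2), 18% of the primary outcome missing (4.6). Observed outcomes: 0.82 × 29 = 23.8, or 0.82 × 28 = 23.0. The size of the modified intention-to-treat set is not given, so n = 23–29 was used.
- Baseline to follow-up correlation 0.3 and SD 7.89 (4.1). The SD does not affect type I error.
- Sites: the plan was that "222 inpatients with BPD will be recruited from seven centres in England". The number that recruited is not stated, so 4, 7 and 10 were tried.

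**Assumptions**
- Site intraclass correlation (ICC) 0–0.2; the SAP gives no value.
- Allocation is in the model, as its purpose requires.
- Large-sample inference is one of several fits that the text allows.

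**Step 1: the stated 5%.** ANCOVA with allocation and baseline, using t on n − 3 df, has size exactly 5% under normal errors.

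**Step 2: closed form with no site variance and no site term estimated**
- Correct residual variance but z reference: 2·P(t[n−3] > 1.96) = 6.3% at n = 24 and 6.1% at n = 28.
- ML variance and z reference: 2·P(t[n−3] > 1.96·√((n−3)/n)) = 8.1% at n = 24 and 7.6% at n = 28.
- Interval width relative to the exact one: 1.96·√(21/24)/t(0.975, 21) = 1.833/2.080 = 0.88 at n = 24, and 1.96·√(25/28)/t(0.975, 25) = 1.852/2.060 = 0.90 at n = 28. The interval is 10–12% too narrow.

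**Step 3: null simulation with the random site effect estimated, no imputation** (8,000–15,000 runs per setting, Monte Carlo SE about 0.2–0.3 points)

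| Fit | Type I error |
|---|---|
| ML, z; 7 sites, n = 24 | 8.6–9.3% |
| ML, z; 7 sites, n = 28 | 7.9–9.1% |
| ML, z; 7 sites, n = 23–29 | 7.7–9.6% |
| ML, z; 4 or 10 sites, n = 24 or 28 | 7.9–9.2% |
| REML, z; all settings | 6.5–7.7% |
| REML, t on n − 3 df | 5.3–6.4% |
| REML, t on n − sites − 2 df | 5.0–5.8% |

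At n = 24 with zero site variance the build-up is 5% (exact t), 6.3% (z for t), 8.1% (ML variance as well), then 9.0–9.3% (site variance estimated as well, 7 sites).

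**Step 4: the stated primary analysis, with imputation.** n = 28, 5 outcomes missing (5/28 = 17.9%), predictive mean matching, m = 5, Rubin pooling with large-sample df, 8,000 runs:
- ML: 7.3–7.5% with 5 donors, 8.6% with 1 donor.
- REML: 6.2–6.4% with 5 donors, 7.6% with 1 donor.

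**Step 5: the source of the excess under imputation.** A separate simulation with the same design, 7 sites and 5 donors (2,500 runs, SE about 0.5 points), at ICC 0 and 0.1:

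| Analysis | ICC 0 | ICC 0.1 |
|---|---|---|
| ANCOVA, no site effect, large-sample Rubin df | 7.1% | 6.2% |
| REML, random site, same pooling | 7.4% | 6.3% |
| ML, random site, same pooling | 8.5% | 7.4% |
| REML, random site, Barnard-Rubin df | 5.6% | 4.9% |

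Once the data are imputed, the random effect under REML adds 0.1–0.3 points to plain ANCOVA. ML adds a further 1.1 points. Most of the rest goes when Barnard-Rubin df are used.

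**The case against.** The strongest reply is that this is unspecified detail, not an error. Section 6.7 fixes the outcome, time point, covariate, random effect and analysis set, and nothing in it rules out REML with small-sample degrees of freedom. That is true, and it limits the claim. The plan does not prescribe an invalid test; it permits one.

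A reader might infer that the primary test will run at 8–9%. The documents do not support that. They name only the software, so ML with z is an assumption, and the 8–9% describes a complete-case fit. Complete cases are the stated sensitivity analysis, although section 4.6 also has a rule that leads to them if the missing-completely-at-random test is satisfied. A reader might also blame the random effect alone. Step 5 shows that under imputation the pooling degrees of freedom and ML account for most of the excess.

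It can also be said that the SAP calls its evidence inconclusive and urges caution throughout, so no confirmatory claim turns on 7% versus 5%. This bears on severity. It does not remove the point, because that caution is about low power, which gives wide but valid intervals; here the intervals would be too narrow. It would go too far, however, to say that the trial makes these intervals its main output. Section 4.3 says only that they accompany each p-value or effect.

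**Conclusion.** The point holds as a gap that should be closed. With a random-site model on about 23–29 patients and no small-sample inference specified, the 5% level and 95% coverage of section 4.3 are not secured.

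If large-sample inference is used, type I error is about 8–9% (ML with z) or 6.5–7.7% (REML with z) in the complete-case fit, and about 6–8.5% in the imputed primary analysis with large-sample Rubin degrees of freedom. With small-sample degrees of freedom it is about 5–6%.

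These figures assume normal errors, an ICC of 0–0.2 and 4–10 sites (7 for the breakdown in step 5). The complete-case results changed little across ICC, number of sites and n = 23–29. The imputed results were obtained at n = 28 only and depend on the number of donors, which the SAP does not give.

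**What to change.** Add to section 6.7, and apply to the secondary models in 6.8:
- Models are fitted by REML, with Kenward-Roger or Satterthwaite degrees of freedom for the treatment effect.
- If the site variance is estimated at zero, the ordinary ANCOVA with t-based inference is reported.
- Imputations are pooled with Barnard-Rubin small-sample degrees of freedom (also stated in 4.6).

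Kenward-Roger and Satterthwaite were not themselves simulated; the nearest case tested, REML with t on n − sites − 2 df, gave 5.0–5.8%. Before sign-off, the statistician should confirm that the chosen method runs with multiply imputed data in the named software.

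The cost is a few lines of text and some model options, with no new data and no change to the treatment effect being estimated. Intervals would be up to about 10–15% wider than large-sample ones (for example 1/0.88 = 1.14 at n = 24 against ML with z).

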6.8 ANALYSIS OF SECONDARY OUTCOMES

All secondary outcome measures are continuous measures and will be analysed as the primary outcome model with a GLM to assess the differences between the means of the treatment groups. The baseline measure scores of the associated outcome will be included in the models as covariates to account for the baseline scores. The BARS measure was not applicable at baseline, therefore independent t-test models will be run on that measure at 3 and 6 months.

Secondary outcomes include the ZAN-BPD at 3 months, and all other secondary measures (listed in table 2) at 3 and 6 months (other than the screening tools and health economic measures).

6.9 SUBGROUP ANALYSES

Subgroup analyses would have been considered if the trial had of reached the recruitment target, however with such little data subgroup analysis would be inappropriate. Descriptive statistics of the primary outcome variable will be presented by the below subgroups:

- Ward type
- Allocation treatment 'guess' (see section 6.10 below)
- Co-existing clinical diagnosis of antisocial personality disorder

6.10 SENSITIVITY ANALYSES OR MODEL TESTING

Some exploratory sensitivity analysis will be conducted; however, this will be limited due to the small sample. Sensitivity analysis results and interpretation, as with the main analysis, should be treated with caution due to the small sample and lack of statistical power.

Sensitivity analysis may be required around any assumptions made for the primary analysis (e.g. outliers, data distributions) but only if necessary. Complete case analysis will be conducted on the primary and secondary data models to check the impacts of multiple imputation on the results at 6 and 12 months.

As indicated, primary and secondary outcomes will firstly be analysed as a mITT analysis. Sensitivity analysis will be carried out on a per protocol analysis (participants who took trial medication, at least until the first follow-up at 3 months) at 6 and 12 months on the primary outcome.

A sensitivity analysis around treatment arm allocation perception will be conducted. This separates into two parts (blinded analysis and unblinded analysis). Firstly, blinded, we will look at the 'view of allocation' i.e. did their view of whether they had placebo or active impact on Zan-BPD scores. For both the assessor and patient, ZAN-PBD scores, will be summarised descriptively, split by 'view of allocation arm' (regardless of what they actually had). For participants the primary outcome model will be run with this variable included to assess any impacts on the scores. In addition, patients view of their allocation and whether they discontinued from study medication, and if so at what time point, will be presented descriptively. This will be conducted on the mITT data set and the per protocol set.

Subsequently, following all blinded analysis being conducted, statistics of numbers of patients and assessors that correctly guessed their allocation will be presented, and in which direction (i.e. thought they were on placebo and were right or wrong or thought they were on active and were right or wrong).

Finally, a sensitivity analysis that adjusts any difference seen between treatment arms according to whether the participant reported 'lethargy/lassitude', as measured by the ANNSERS, will be conducted. This will be carried out by including the ANNSERS item for 'lethargy/lassitude' as an independent variable in the analysis model on the ZAN-BPD at 3 and 6 months. This will be on both the mITT and per protocol analysis sets.

Descriptive statistics will also be presented for the number of participants who discontinued trial medication and were then prescribed Clozapine while continuing in the trial. These will be summarised as counts and percentages presented overall and by allocation group.

